2.3. Study Design

Overview of Key Study Design Features	
Design Features:	
 • Multi-centre, randomized, double blind, double dummy, 3-arm parallel group study to compare Umeclidinium/Vilanterol, Umeclidinium, and Salmeterol in subjects with chronic obstructive pulmonary disease (COPD). • Approximately 3232 subjects will be screened, such that 2424 subjects will be randomized and approximately 2181 evaluable subjects complete the study. • Eligible subjects will be stratified by country, long-acting bronchodilator usage during the run-in (none or one long-acting bronchodilator per day) and activity subset (activity subset or no activity subset), and randomized in a ratio of 1:1:1 to UMEC/VI inhalation powder (62.5/25 mcg once daily) administered via the ELLIPTA inhaler, or UMEC (62.5 mcg once daily) administered via the ELLIPTA or salmeterol (50 mcg BID) administered via the DISKUS. Note the activity subset was only included as a randomisation stratification group for logistical purposes. • A subset of subjects up to 150 per treatment arm will undergo assessment of their physical activity measured through a physical activity monitor (Actigraph GT9X) worn for 7 days from Screening (Visit 1), for 7 days from Randomisation (Visit 2), 7 days from Visit 3, and for 7 days prior to last clinic Visit (Visit 5). • The total duration of subject participation in the study will be approximately 29 to 35 weeks consisting of 6 weeks pre-screening if necessary, 4 weeks run-in, 24 week treatment and one week Follow-Up.
Dosing :	
 • The following study medications will be used in this study: 
 - UMEC/VI 62.5/ 25mcg administered via ELLIPTA - UMEC 62.5 mcg administered via ELLIPTA - Salmeterol 50 mcg administered via DISKUS - Placebo via ELLIPTA - Placebo via DISKUS 
Subjects will be instructed to take one dose of medication each morning from the ELLIPTA (one inhalation equals one dose), and one dose in the morning and one in the evening from the DISKUS.
 
The ELLIPTA will provide a total of 30 doses and the DISKUS will provide a total of 60 doses.

Overview of Key Study Design Features	

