7.2.5.1. Statistical Methodology Specification

TDI, E-RS, SGRQ-C and CAT Scores

Secondary Statistical Analysis
Endpoints

 • SAC TDI focal score • Assessment of respiratory daily symptoms using E-RS and its subscales • Change from baseline in SGRQ • Change from baseline in CAT
Model Specification, Checking and Results Presentation

 • Similar to trough FEV1 in Section 7.1.5.1. • For TDI one model will be fitted with a dependent variable of TDI and BDI in place of baseline. • For E-RS and subscales, all 4-weekly mean scores will be included in the analysis.

Responders according to TDI, E-RS, SGRQ-C and CAT Scores

Secondary Statistical Analysis
Endpoints

 • Proportion of responders according to TDI focal score • Proportion of responders according to E-RS total score • Proportion of responders according to E-RS Breathlessness score • Proportion of responders according to E-RS Cough & Sputum score • Proportion of responders according to E-RS Chest Symptoms score • Proportion of responders according to SGRQ total score • Proportion of responders according to CAT score
Model Specification

 • The proportion of responders will be analyzed using a generalized linear mixed model with treatment as an explanatory variable and visit, baseline score, stratum (no. of bronchodilators per day during run-in), geographical region, visit by baseline score and visit by treatment interactions included as covariates. • Model using proc glimmix with; random visit / subject=subject*period residual type=un statement to account for repeated visit; • For TDI the model will use BDI in place of baseline score. • For E-RS the model will use 4 weekly period in place of visit. • This analysis will include all subjects with a non-missing baseline assessment. See Section 10.6.2.3 for details on how to handle missing data.
Model Checking & Diagnostics

 • UMEC will be used as the reference level for treatment for the comparison between UMEC/VI vs. UMEC. Salmeterol will be used as the reference level for treatment for the comparison between UMEC/VI vs. Salmeterol and UMEC vs Salmeterol.

Secondary Statistical Analysis

 Pearson residuals will be plotted by using PLOTS=RESIDUALPANEL option for the model statement in SAS.
Model Results Presentation

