
 The odds ratio, 95% CI and p-value will be presented for UMEC/VI versus UMEC, UMEC/VI versus Salmeterol and UMEC versus Salmeterol.
Summary Results Presentation

 The number and percentage of responders and non-responders at each visit will be summarized on the same table as the analysis results details above.
Sensitivity and Supportive Statistical Analyses

 If the model fails to converge then the analyses will be carried out separately for each visit or 4 weekly period instead.

COPD Exacerbation

Secondary Statistical Analysis
Endpoints

 Time to first on-treatment mild/moderate/severe COPD exacerbation Time to first on-treatment moderate/severe COPD exacerbation Time to first on-treatment severe COPD exacerbation
Model Specification

 Cox's proportional hazards model, 
Terms in the model:
 
Dependent variable: time to first on-treatment mild/moderate/severe exacerbation or moderate/severe exacerbation or severe exacerbation
 
Categorical: treatment group, stratum (no. of bronchodilators per day during run-in) and geographical region.
 
 Use the 'exact' method for handling ties. (If the analysis will not run using the 'exact' method, then the 'Efron' method for handling ties will be used instead.)
Model Checking & Diagnostics

 The proportional hazards assumption for this method of analysis will be examined by obtaining the Kaplan-Meier estimates of the survival function $S(t)$ over time separately for treatment group. Under the assumption of proportional hazard between the treatment groups, $\ln\{-\ln[S(t)]\}$ for the two groups should be parallel to each other and the distance between them constant. If the curves are approximately parallel, then the proportional hazard assumption is not violated. If these curves cross each other or diverge greatly from the assumption of parallel lines, then the assumption is not met. If model fails to converge, model will be investigated excluding the geographical region covariate.

Secondary Statistical Analysis
Model Results Presentation

 The Hazard ratio, 95% CI and p-value will be presented for comparison between UMEC/VI versus UMEC, UMEC/VI versus Salmeterol and UMEC versus Salmeterol.

Secondary Statistical Analysis
Endpoints

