
 Similar to trough FEV1 in Section 7.1.5.1 where Visit is replaced with 4-weekly period. The model will use all available values: 
 Periods defined as Weeks 1-4, 5-8, 9-12, and up to Weeks 21-24 Baseline is defined in Section 5.2 Model will include the period by baseline and period by treatment interaction. Overall treatment effect from the same model using overall main effect on Lsmean statement.
Sensitivity and Supportive Statistical Analyses

 If the assumption of normality for the percentage of rescue-free days is not satisfied, a non-

Secondary Statistical Analysis
parametric analysis of percentage of rescue-free days will be carried out. Hodges Lehman estimates for the median treatment difference and 95% CI based upon a Wilcoxon rank sum test will be used. The p-value will be based on Van Elteren test, an extension to the Wilcoxon rank sum test for two group comparison, stratified by geographical region.

Trough FEV1, FVC and IC

Secondary Statistical Analysis
Endpoints

 • Ratio of trough FEV1 to baseline FEV1 • Trough FVC • Trough IC
Model Specification

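### The covariance line for the responder models blocks on subject-by-period: for the four E-RS endpoints it cannot model repeated measures, and for TDI, SGRQ and CAT its meaning is undefined

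*SAP*

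**What the plan says.** The responder part of SAP Section 7.2.5.1 covers seven endpoints: TDI, E-RS total, three E-RS subscales, SGRQ and CAT. One covariance statement serves all of them: "random visit / subject=subject*period residual type=un statement to account for repeated visit". The fixed effects are treatment, visit, baseline score, stratum and region, with "visit by baseline score and visit by treatment interactions included as covariates". No period term is listed.

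For the diary endpoints the section adds: "For E-RS the model will use 4 weekly period in place of visit". The word period is defined for analysis only as the 4-weekly diary slots. The rescue-medication part of the same section has "Periods defined as Weeks 1-4, 5-8, 9-12, and up to Weeks 21-24", and the eDiary table in Section 10.5.3 uses the same six slots. Section 2.3 describes the design as a "Multi-centre, randomized, double blind, double dummy, 3-arm parallel group study".

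On results, the SAP says: "The odds ratio, 95% CI and p-value will be presented for UMEC/VI versus UMEC, UMEC/VI versus Salmeterol and UMEC versus Salmeterol". It does not say at which visit or period. Responder counts at each visit go in the same table. The fallback is: "If the model fails to converge then the analyses will be carried out separately for each visit or 4 weekly period instead".

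**The concern.** In an R-side RANDOM statement, the SUBJECT= effect defines the block within which records may be correlated. To account for repeated visits, the block must contain all of a subject's visits. Crossing subject with period would suit a crossover trial, where each subject has several treatment periods. Here there is only one.

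If the block holds a single record, the statement cannot do what it says it is for. The responder endpoints are secondary. Under Section 2.4, each can be declared significant at p below 0.05 once the primary comparison succeeds. A covariance line that cannot be run as written leaves the programmer to choose between recoding period, changing the block and invoking the fallback. That makes a prespecified inferential model discretionary.

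**Working it through.** The SAP states no error rate or precision for the responder models, so there is no figure to reproduce. SAS was not run; GLIMMIX behaviour is inferred from the block structure.

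**Inputs.** Three post-baseline visits for TDI, SGRQ and CAT (Weeks 4, 12 and 24; Section 10.1.1). Six 4-weekly periods for E-RS (Section 10.5.3). 2424 randomized 1:1:1 (Section 2.3), so 2424/3 = 808 per arm. Assumed, because the documents do not give it: a within-subject correlation of responder status, ρ, of 0.3 to 0.7.

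**Step 1: records per block.** An unstructured matrix for T time points has T(T+1)/2 parameters, of which T(T−1)/2 are off-diagonal. The off-diagonals need pairs of records within a block.

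| Endpoints | T | Parameters | Off-diagonals | Pairs per subject, block = subject | Pairs, block = subject × time point |
|---|---|---|---|---|---|
| TDI, SGRQ, CAT | 3 | 6 | 3 | 3 | 0 |
| E-RS total and subscales | 6 | 21 | 15 | 15 | 0 |

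For E-RS, the SAP makes the 4-weekly period the time point, so the last column applies. For TDI, SGRQ and CAT there are three readings:

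- Period is a constant treatment-period index: the block equals the subject, and nothing is lost.
- Period is the time point: zero pairs against three off-diagonals, the same fault as for E-RS.
- The variable does not exist: the code errors. That is not non-convergence, so the stated fallback would not strictly apply.

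**Step 2: effect on an odds ratio averaged over time, if records are treated as independent.** With T equally correlated log odds ratios of variance σ², the variance of their mean is (σ²/T)(1 + (T−1)ρ), against σ²/T under independence. The correct-to-naive SE ratio is R = √(1 + (T−1)ρ). The actual size of a nominal 5% test is 2(1 − Φ(1.96/R)).

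| T | ρ | R | Actual size |
|---|---|---|---|
| 3 | 0.3 | √1.6 = 1.26 | 12.1% |
| 3 | 0.5 | √2.0 = 1.41 | 16.6% |
| 3 | 0.7 | √2.4 = 1.55 | 20.6% |
| 6 | 0.3 | √2.5 = 1.58 | 21.5% |
| 6 | 0.5 | √3.5 = 1.87 | 29.5% |
| 6 | 0.7 | √4.5 = 2.12 | 35.6% |

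**Step 3: simulation.** 400 null trials per scenario, two arms of 808, logistic model with time-by-treatment and time-by-baseline terms, comparing independence SEs with subject-clustered SEs.

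| T | Binary ρ | Last time point: SE independent / clustered | Type I | Averaged: SE independent / clustered | Type I |
|---|---|---|---|---|---|
| 3 | 0.36 | 0.1031 / 0.1032 | 5.0% / 5.0% | 0.0596 / 0.0766 | 14.0% / 5.2% |
| 3 | 0.51 | 0.1031 / 0.1032 | 5.8% / 5.8% | 0.0596 / 0.0837 | 15.8% / 4.3% |
| 6 | 0.52 | 0.1031 / 0.1031 | 4.8% / 4.8% | 0.0421 / 0.0781 | 29.7% / 6.2% |
| 6 | 0.66 | 0.1031 / 0.1032 | 4.8% / 4.8% | 0.0421 / 0.0864 | 33.8% / 4.8% |

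The simulated SE ratios for the averaged effect (for example 0.0781/0.0421 = 1.86 at ρ = 0.52) agree with the formula (√(1 + 5 × 0.52) = 1.90). The single-time-point contrast is essentially unaffected.

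**The case against.** The strongest reply is that planned inference hardly changes. Several features point to odds ratios by visit: the visit-by-treatment term, responder status defined per visit or per 4-weekly period (Section 10.5.3), counts by visit in the same table, and a fallback by visit. Where the SAP wants an overall effect it says so, as for rescue use, where an overall LS-means effect is requested. For by-visit odds ratios the SE is the same to three decimals, and the fallback would give nearly the same estimates. Nor is much lost on incomplete data: Section 10.6.2.3 counts a subject as a non-responder from the last available assessment onward, so only intermittent gaps stay missing. This all stands and limits the practical harm.

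A reader might infer from Step 2 that the responder tests run at a type I error of about 30%. The documents do not support that. It needs an odds ratio pooled over periods, which the responder section does not plan, and a correlation the documents do not give. Pooling is not excluded either, because the time point of the odds ratio is not stated.

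A reader might also infer that all seven endpoints are shown to be affected. That too goes beyond the text: for TDI, SGRQ and CAT the outcome depends on an undefined variable, and a constant code would be harmless. A separate constant called period would rescue E-RS as well, but the SAP defines no such variable and already uses the name for the diary slots.

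Finally, the intent is plain from the statement's own purpose clause. That makes the correction easy, but it does not make the line correct.

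**Conclusion.** Wrong as written; a minor to moderate correction. For the four E-RS responder endpoints, the SAP's own wording leaves one record per block, so the unstructured repeated-measures model cannot be estimated as specified. For TDI, SGRQ and CAT the finding is an undefined block variable, not demonstrated independence.

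The size depends on what is reported. Odds ratios by visit or period are nearly unchanged. A pooled odds ratio would have a standard error too small by a factor of about 1.3 to 1.6 with three visits and 1.6 to 2.1 with six periods. These factors rest on an assumed, equal within-subject correlation of 0.3 to 0.7 and on the software treating the records as independent instead of failing. The primary MMRM has its own covariance specification and is not touched.

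**What to change.** In the responder part of Section 7.2.5.1:

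- For TDI, SGRQ and CAT, use `random visit / subject=subject residual type=un`.
- For E-RS, use `random period / subject=subject residual type=un`, with period defined as the six 4-weekly slots.
- State that subject is the unique subject identifier.
- State the time point of the reported odds ratio, confidence interval and p-value for each endpoint.
- Reserve the separate analyses by visit or period for genuine non-convergence of the corrected model.

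The cost is a few lines of SAP text, settled before unblinding. Data collection, sample size and trial conduct are unaffected. In the simulation, subject-clustered standard errors gave a type I error of 4.3% to 6.2% for both single-time-point and averaged contrasts.

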7.3. Exploratory Efficacy Analyses

7.3.1. Endpoint / Variables

- 1) Annual rate of on-treatment mild/moderate/severe exacerbations
- 2) Annual rate of on-treatment moderate/severe exacerbations
- 3) Mean number of inhalations of rescue use per day (using eMDI)
- 4) Percentage of rescue-free days (using eMDI)
- 5) To compare physical activity levels, ER-S, rescue medication use, exacerbations and mortality in subjects with and without a CID
- 6) Physical activity

7.3.2. Summary Measure

- 1) Rate ratio
- 2) Rate ratio
- 3) Mean change from baseline
- 4) Mean change from baseline
- 5) Mean change from baseline
- 6) Mean change from baseline

7.3.3. Population of Interest

The exploratory analyses will be based on the ITT population apart from the physical activity endpoint and deterioration status at 24 weeks to predict the outcome of physical activity levels, which will be based on the AM population.

7.3.4. Strategy for Intercurrent (Post-Randomization) Events

- All Endpoints will use the same strategy for intercurrent events as defined in Section [7.1.4.](#)

7.3.5. Statistical Analyses / Methods

Details of the planned displays are provided in [Appendix 8: List of Data Displays](#) and will be based on GSK data standards and statistical principles.

Unless otherwise specified, endpoints / variables defined in Section [7.3.5.1](#) will be summarised using descriptive statistics, graphically presented (where appropriate) and listed.

7.3.5.1. Statistical Methodology Specification

Exploratory Statistical Analyses
Endpoints

 • Annual rate of on-treatment mild/moderate/severe exacerbations • Annual rate of on-treatment moderate/severe exacerbations
Model Specification

 • Generalized linear model assuming a negative binomial distribution,

Exploratory Statistical Analyses

Terms in the model:
 
 Response: number of on-treatment mild/moderate/severe exacerbations or moderate/severe exacerbations per subject Categorical: treatment group, exacerbation history (≤ 1, ≥ 2 of severity endpoint), stratum (no. of bronchodilators per day during run-in) and geographical region. Offset: logarithm of time on treatment
Model Checking & Diagnostics

 • The fit of the regression models will be examined using “Q-Q” plots of the standardized residuals. Interpretation of these plots will be aided by the addition of simulated envelopes as proposed by Atkinson (Atkinson, 1985). Should the model not fit with all specified covariates (fixed effects with very large estimates/variances) then geographical region will be dropped from the model. • If there are concerns over model fit then an over dispersed poisson model will be investigated.
Model Results Presentation

 • Treatment group mean annual exacerbation rates, treatment rate ratio and associated 95% CI will be presented and p-values will be presented. 
Analysis is limited by number of moderate and severe exacerbations possible before withdrawal to the study and due the assumption they continue at this rate post withdrawal. Output to be appropriately footnoted.

Exploratory Efficacy Statistical Analyses
Endpoints

 • Mean number of occurrences of rescue use per day (using eMDI) • Percentage of rescue-free days (using eMDI)
Model Specification, Checking and Results Presentation

 • Similar to trough FEV1 in Section 7.1.5.1 excluding visit from the model 
 • Baseline is defined in Section 5.2

Exploratory Statistical Analyses
Endpoints

 • Deterioration Status at Day 30 to predict short term outcomes: 
 ○ ER-S ○ Rescue medication use (Mean number of inhalations of rescue use per day (using eDiary)) ○ Mortality ○ Hospitalised Exacerbations
Model Specification

 • Change in E-RS and mean number of inhalations of rescue use per day will be compared between subjects who have and have not experienced deterioration up to and including day 30, using a MMRM model. The following covariates will be included in the model: treatment,

Exploratory Statistical Analyses
 
deterioration status at day 30 , baseline, geographical region, stratum (no. of bronchodilators per day during run-in), 4-weekly period, deterioration status at day 30 weeks by 4 weekly period, and 4-weekly period by baseline interactions. Data will only be included post visit 3.
 
 The time to first hospitalized exacerbation after day 30 and time to mortality after day 30 will be presented for subjects with and without deterioration at day 30. The actual time to post day 30 hospitalised exacerbation and mortality will be analysed using a Cox’s proportional hazards models, with covariates treatment group, stratum (no. of bronchodilators per day during run-in) and geographical region. and deterioration at day 30.

Model Checking & Diagnostics
 
 The Kenward and Roger method (KR) for approximating the denominator degrees of freedom and correcting for bias in the estimated variance-covariance of the fixed effects will be used. In the event the model fails to run using the KR method, then the residual method will be used instead. Distributional assumptions underlying the model used for analysis will be examined by obtaining a normal probability plot of the residuals and a plot of the residuals versus the fitted values (i.e. checking the normality assumption and constant variance assumption of the model respectively) to gain confidence that the model assumptions are reasonable.

Model Results Presentation
 
 For E-RS and mean number of inhalations of rescue use per day the adjusted means, pairwise differences, p-values and 95% confidence limits for the deterioration status differences will be summarised at visit 4 and visit 5 only. For mortality and hospitalized exacerbations, the Hazard ratio, 95% CI and p-value will be presented for the comparison between deterioration status.

Summary Results Presentation
 
 A summary of subjects who have and have not experienced a first deterioration at day 30 will be presented.

Exploratory Statistical Analyses

Endpoints
 
Physical activity
 
 Change from baseline in step count Change from baseline in light activity duration Change from baseline in moderate to vigorous physical activity duration Change from baseline in total energy expenditure

Model Specification
 
 The dataset containing the mean value for each subject-visit will be used to look at differences between baseline, Week 1, Week 4 and Week 24. MMRM will be used to model each activity variable against the treatment group variable including data recorded at each of baseline, Week 1, Week 4 and Week 24.

• Other covariates included will be the mean of the activity monitor variable at baseline and smoking status.
Model Checking

• The physical activity endpoints will be plotted in histograms to view their distributions and enable possible sensitivity analyses.
Model Results Presentation

• Estimated mean change from baseline for each treatment group will be calculated from the model and displayed with their associated standard errors. The estimated treatment difference will also be presented together with 95% confidence intervals (CIs) for the difference and p-value.
Summary Results Presentation

• Summaries will include the means and standard deviations of the activity monitor variables at the four time points by treatment group.
Sensitivity and Supportive Statistical Analyses

• If the histogram for change in step count or light activity duration or moderate to vigorous physical activity duration or total energy expenditure is not normally distributed, a transformation of the variable may be considered. If the MMRM analysis shows that the model is ill-fitting then a Mann-Whitney test (non-parametric t-test) will be used to look at the change in activity monitor outputs between each treatment group at Week 1, Week 4 and Week 24.

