
 • Ratio of trough FEV1 to baseline FEV1 at Week 24 will be analysed for the ITT population using a mixed model repeated measures (MMRM) including data recorded at each of Week 4, Week 12 and Week 24. The model will have a response of log (Trough FEV1/Baseline FEV1) with covariates of log (baseline FEV1), geographical region, stratum (no. of bronchodilators per day during run-in), visit, treatment, visit by log (baseline FEV1) and visit by treatment interactions, where visit is nominal. Results will be back transformed to provide point estimates for the ratios. • Trough FVC and Trough IC endpoints above will be analyzed using the same methodology as the primary analysis of trough FEV1 (detailed in Section 7.1) using all available FVC or IC data recorded at Weeks 4, 12 and 24 and with relevant baseline. Baseline defined in Section 5.2. 
The following will apply for all the endpoints FEV1, FVC and IC:
 
 • The Kenward and Roger method (KR) for approximating the denominator degrees of freedom and correcting for bias in the estimated variance-covariance of the fixed effects will be used. • In the event the model fails to run using the KR method, then the residual method will be used instead. • An unstructured covariance structure for the R matrix will be used by specifying 'type='UN' on the REPEATED line.
Model Checking & Diagnostics

 • Model assumptions will be applied but appropriate adjustments may be made based on the data. • Normality assumptions underlying the model used for analysis will be examined by obtaining a normal probability plot of the residuals and a plot of the residuals versus the fitted values (i.e. checking the normality assumption and constant variance assumption of the model respectively) to gain confidence that the model assumptions are reasonable. • If there are any departures from the distributional assumptions, alternative models will be explored using appropriate transformed data.
Model Results Presentation

 • Least squares (LS) mean and LS mean changes from baseline with their corresponding

Secondary Statistical Analysis

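### The physical-activity fallback is an unadjusted Mann-Whitney test of raw change with no estimate or confidence interval; a baseline-adjusted rank analysis with a Hodges-Lehmann interval would improve it at little cost

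*SAP*

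**What the plan says.** SAP section 7.3.5.1 models each of the four activity variables (step count, light activity duration, moderate-to-vigorous duration, total energy expenditure) with an MMRM. On adjustment it says: "Other covariates included will be the mean of the activity monitor variable at baseline and smoking status". On output it says: "The estimated treatment difference will also be presented together with 95% confidence intervals (CIs) for the difference and p-value".

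Under the sensitivity and supportive heading of the same section, if the change is not normally distributed, "a transformation of the variable may be considered". The next step, if the MMRM proves to fit badly, is that "a Mann-Whitney test (non-parametric t-test) will be used to look at the change in activity monitor outputs between each treatment group". It is applied to change at each of Weeks 1, 4 and 24. No covariate, stratification, estimate or interval is named for it.

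Two other parts of the SAP are relevant, both in section 7.2.5.1:

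- The rank fallback for percentage of rescue-free days specifies an estimate: "Hodges Lehman estimates for the median treatment difference and 95% CI based upon a Wilcoxon rank sum test will be used". Its p-value comes from a Van Elteren test, described as "an extension to the Wilcoxon rank sum test for two group comparison, stratified by geographical region".
- For the FEV1 ratio to baseline, "The model will have a response of log (Trough FEV1/Baseline FEV1"), with log baseline as a covariate and results back-transformed.

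**The concern.** Moving from the MMRM to a two-group test of raw change gives up three things: adjustment for baseline activity and smoking status, the joint likelihood handling of visits and missing sessions, and a defined effect measure. Subtracting baseline is not the same as adjusting for it. Unless the correlation between visits is very high, raw change carries avoidable noise.

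The subset has at most 150 subjects per arm (section 2.3). The validity rule of at least 23 hours' wear on at least 3 days per session (section 10.5.3) will reduce it further. At that size efficiency matters, and a bare rank-test p-value would say little about how far activity changed. At stake is how well an exploratory question can be read; no confirmatory claim depends on it.

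**Working it through.** **What the SAP fixes.** Up to 150 per arm, 1:1:1 allocation (section 2.3). It states no effect size, SD, baseline-to-follow-up correlation (ρ) or power for physical activity, so there is no figure to reproduce. The inputs below are assumptions. Two-sided 0.05 is used for illustration; section 2.4 states 0.05 only for primary and secondary endpoints.

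**Step 1: normal data, one visit, 150 per arm, SD 1 at each visit.**

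- Baseline-adjusted analysis: residual SD = √(1−ρ²).
- Raw change: SD = √(2(1−ρ)).
- Variance ratio, adjusted to raw change: (1−ρ²)/(2(1−ρ)) = (1+ρ)/2.
- Mann-Whitney efficiency relative to the t-test under normality: 3/π ≈ 0.955.
- Relative sample size needed by the fallback: 1/[((1+ρ)/2)(3/π)].
- Effect δ set so that the adjusted analysis has 80% power: δ = (1.96+0.84)·√(1−ρ²)·√(2/150).

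Worked case, ρ = 0.5: δ = 2.80 × 0.866 × √(2/150) = 0.280. Effective n per arm for Mann-Whitney = 150 × 0.955 = 143.2. SE = 1.000 × √(2/143.2) = 0.118. Power = Φ(0.280/0.118 − 1.96) = Φ(0.41) = 66%.

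| ρ | adjusted SD | change SD | relative n | Mann-Whitney power (adjusted analysis: 80%) |
|---|---|---|---|---|
| 0.3 | 0.954 | 1.183 | 1.61 | 60% |
| 0.5 | 0.866 | 1.000 | 1.40 | 66% |
| 0.7 | 0.714 | 0.775 | 1.23 | 71% |
| 0.8 | 0.600 | 0.632 | 1.16 | 74% |
| 0.9 | 0.436 | 0.447 | 1.10 | 76% |

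**Step 2: non-normal errors, where the fallback is more likely to be used.** Simulation at 150 per arm, same δ, 3000 runs per cell, ρ = 0.5 / 0.7 / 0.8.

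| errors | Mann-Whitney on change | normal ANCOVA | follow-up ranks adjusted for baseline rank |
|---|---|---|---|
| t(3) | 82 / 89 / 92% | 82 / 82 / 80% | 93 / 90 / 88% |
| log-normal | 90 / 98 / 99% | 81 / 82 / 82% | 99 / 98 / 96% |

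Mann-Whitney type I error was 4.7% to 5.6% across all scenarios, normal ones included. In these two settings the plain test equals or beats the model it replaces. Against an analysis that ranks the follow-up value, it loses 9 to 11 points at ρ = 0.5, is about level at 0.7 and gains 3 to 5 points at 0.8.

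**Step 3: rank the change instead, and adjust it for baseline rank.** Simulation at 100 per arm. Effects are assumed and differ between rows, so compare within rows only.

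| data | Mann-Whitney on change | change ranks adjusted for baseline rank | log-ratio ANCOVA |
|---|---|---|---|
| log-normal (log SD 0.55, 15% increase), ρ = 0.6 | 48% | 53% | 61% |
| t(3) errors, ρ = 0.7 | 84% | 92% | 65% |
| normal, ρ = 0.7 | 67% | 74% | not compared |

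Type I error was 4.3% to 5.3%. The adjusted rank analysis gains 5, 8 and 7 points over the plain test in these rows. The log-ratio model gains 13 points in the first row and loses 19 in the second.

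**Limits.** Each simulation uses a single visit. None includes smoking status or missing sessions, so the cost of dropping those is not quantified.

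**The case against.** The strongest reply has four parts.

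- **The test is valid and minor.** Randomisation protects it, change already subtracts baseline, and the endpoint is exploratory and outside the testing procedure of section 2.4. This stands in full and sets the severity.
- **A transformation comes first.** A reader might infer that the step is empty, because a change score can be negative and so cannot be logged. The wording does not compel that: the variable may be the activity measure itself, and some transformations accept negative values. What remains is that the step is optional and unspecified.
- **Power is not lost in general.** A reader of Step 1 might infer that it is. Step 2 shows otherwise: with heavy-tailed or skewed errors the plain test can beat the normal model. The SAP gives neither the correlation nor the error distribution needed to say which case applies.
- **The MMRM estimates are not shown to be withdrawn.** A reader might infer that only a p-value would be reported. But the test is listed as supportive, means and SDs by arm are promised, and the activity analysis tables (2.71, 2.73, 2.75, 2.77) and least-squares mean figures (2.44 to 2.47) carry no condition. Still, if the model is judged ill-fitting, its estimates are the ones in doubt, and none is specified to go with the test used instead.

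It would also be tempting to delete the rank test and use the FEV1 log-ratio model throughout. Step 3 does not support that: the log-ratio model wins on log-normal data and loses with t(3) errors. It also cannot take zeros, which may occur in moderate-to-vigorous duration. The rescue-free-days method is not a complete cure either, since it stratifies by region and does not adjust for baseline.

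**Conclusion.** The point holds as a minor improvement. As written, the fallback omits the covariates of the main activity model and specifies no estimate or interval, although the SAP specifies both for its other rank fallback. This affects efficiency and reporting in an exploratory subset of up to 150 per arm. It does not indicate bias or an inflated type I error.

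The size of any power loss cannot be fixed from the SAP. Under assumed normal data it is about 4 to 20 points from 80%, for ρ from 0.9 down to 0.3. Under assumed heavy-tailed or skewed errors there may be none relative to the normal model. The firmer result is that ranking the change and adjusting for baseline rank matched or beat the plain test in the scenarios tried, within simulation error. The reporting gap does not depend on any of these assumptions.

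**What to change.** In the physical-activity part of section 7.3.5.1:

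1. Keep a rank-based fallback, but replace the unadjusted Mann-Whitney test with a rank analysis of change at each visit, adjusted for baseline rank and smoking status. State that the change is what is ranked; ranking the follow-up value did less well than the plain test at ρ = 0.8 with non-normal errors.
2. Beside it, report the Hodges-Lehmann median difference with 95% CI for each pairwise comparison, as the rescue-free-days fallback already does.
3. Optionally, define the transformation step: where all values are positive and residuals show right skew, fit the MMRM of log(value/baseline) with log baseline as covariate and report back-transformed ratios, following the FEV1 ratio specification in 7.2.5.1. This should be an option, not a blanket replacement.

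The cost is a few lines of SAP text and slightly more programming. The Hodges-Lehmann interval is itself unadjusted, so it may occasionally disagree with the adjusted p-value near the threshold; a footnote should say so.
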